Urogenital symptoms may include vaginal itching, burning, dryness, dyspareunia (difficult or painful sexual intercourse), dysuria (painful or difficult urination), nocturia (waking at night to urinate), incontinence (the involuntary loss of urine), urine frequency, urine urgency, and UTI.

Primary Objective	Evaluation of the subjective effects of fCO ₂ laser therapy on overall urogenital symptoms.
Secondary Objective	Assess vaginal pH and bacteria, overall vaginal health, urinary symptoms, sexual function, UTI frequency, and mental health status.
Primary Outcome	The mean and median response to treatment as measured by the Patient Global Impression of Improvement (PGI-I) questionnaire
Secondary Outcomes	Change in vaginal pH and overall vaginal health on physical examination as measured by the Vaginal Health Inventory Score (VHIS) Change in urinary symptoms as measured by the Questionnaire for Urinary Incontinence Diagnosis (QUID), OAB symptoms as measured by the Overactive Bladder Questionnaire-Short Form (OAB-q SF), cough stress test and voiding diaries Change in sexual function, including dyspareunia symptoms, as measured by the Female Sexual Function Inventory (FSFI) Change in the frequency of UTI occurrences Change in mental health status as measured by the Generalized Anxiety Disorder Questionnaire (GAD-7) and Patient Health Questionnaire (PHQ-8) Change in life and sexual impact of vulvovaginal skin symptoms as measured by the Incontinence Quality of Life Questionnaire (I-QOL) Change in the presence of lactobacillus, assessed by vaginal swab
Primary Endpoint	Week 16 (4 weeks post-treatment).
Secondary Endpoints	Primary and secondary outcomes will be evaluated again at Visit 4 (6-month follow-up) Primary and secondary outcomes will be evaluated again at Visit 10 (36-month follow-up)

SECTION II: METHODOLOGY

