This is a prospective observational study of patients undergoing vaginal treatment with the fCO₂ laser for various urogenital symptoms. We anticipate enrolling approximately 100 women in this study. The majority of patients are expected to be recruited from the WUC and private Urology offices. Informed consent will be obtained before any study activities are conducted. Women who meet all of the eligibility criteria will be enrolled in the study. Three treatments with the fCO₂ laser to the vagina will be performed, approximately six weeks apart. The patient will follow up every three months for the first year, then every six months for the following two years, for a total of three years of follow-up.

At each follow-up visit, the patients will complete specified questionnaires. The patient will be offered a repeat treatment at 1, 2 and 3 years if initial treatment efficacy has decreased. A pelvic examination will be performed at Visits 4 (6-month follow up), 6 (12-month follow up), 8 (24-month follow up), and 10 (36-month follow up) and the clinician will complete a cough stress test and the VHIS, including vaginal pH.

Patients will be advised to refrain from:

- vaginal intercourse for 24 hours prior to all visits.
- starting vaginal or systemic hormone therapy or use of new vaginal lubricants during the first six months of the study.
- starting any other preventative therapies for UTIs including antibiotic suppression, cranberry supplements, or d-mannose during the first six months of the study.
- starting any new treatments (i.e. pharmacologic, physical therapy) for overactive bladder (OAB) or stress urinary incontinence (SUI) during the first six months of the study.

Study patients will not be compensated for their participation in the trial. However, all research related activities, specified on the table of events, will be provided at no cost to the study patient.

Inclusion/Exclusion Criteria

Inclusion criteria:

- Female
- ≥18 years and ≤90 years of age
- One or more of the following indications for fCO₂ laser treatment:
 - Genitourinary symptoms of menopause, including after natural, medically-induced, or surgical menopause
 - Vaginal dryness, burning, itching, or dyspareunia not related to menopause
 - Recurrent UTIs, defined as 4 or more in a year
 - Overactive bladder
- Must sign the informed consent form
- Must be willing to comply with the study protocol

Exclusion criteria:

- Contraindications to fCO₂ laser treatment, such as:

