Visit 2 – Treatment 2 (6 weeks +/- 2 weeks after Visit 1)

Current medications and AEs will be assessed. Urine dipstick, and urine culture will be performed, if indicated. UTI symptoms will be assessed. Urine pregnancy test will be done in women of childbearing capability. The patient will complete a PGI-I for symptom improvement, VSQ, I-QOL, QUID, OAB-q SF, FSFI, GAD-7 and PHQ-8. A vaginal exam, including a cough stress test and VHIS, will be performed. A vaginal swab will be collected for wet mount and examined microscopically for presence of lactobacillus. The fCO₂ laser treatment will be performed, and patient will score discomfort using the VAS. The provider will score the difficulty of administering the treatment using the VAS. The patient will complete a three-day voiding diary within 1 week prior to Visit 3, which will be collected at Visit 3.

Visit 3 – Treatment 3 (6 weeks +/- 2 weeks after Visit 2)

Current medications and AEs will be assessed. Urine dipstick, and urine culture will be performed, if indicated. UTI symptoms will be assessed. Urine pregnancy test will be done in women of childbearing capability. The patient will complete a PGI-I for symptom improvement, VSQ, I-QOL, QUID, OAB-q SF, FSFI, GAD-7 and PHQ-8. A vaginal exam, including a cough stress test and VHIS, will be performed. A vaginal swab will be collected for wet mount and examined microscopically for presence of lactobacillus. The fCO₂ laser treatment will be performed, and patient will score discomfort using the VAS. The provider will score the difficulty of administering the treatment using the VAS. The patient will complete a three-day voiding diary within 1 week prior to Visit 4, which will be collected at Visit 4.

In the event that scheduling difficulties result in treatment visits out of window, the treatment visits will take place no less than 4 weeks apart.

Phone Call (4 weeks +/- 1 week after Visit 3)

Research staff will contact the patient by phone to assess for AEs and administer the PGI-I for overall urogenital symptoms and Perception of Monetary Value.

Visit 4 - 6 Month Follow up (3 months +/- 2 weeks after Visit 3)

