Current medications and AEs will be assessed. Urine dipstick, and urine culture will be performed, if indicated. UTI symptoms will be assessed. Urine pregnancy test will be done in women of childbearing capability. The patient will complete a PGI-I for symptom improvement, VSQ, I-QOL, QUID, OAB-q SF, FSFI, GAD-7 and PHQ-8. A vaginal exam, including a cough stress test and VHIS, will be performed. A vaginal swab will be collected for wet mount and examined microscopically for presence of lactobacillus. If the patient feels her symptoms have returned and she requests a repeat treatment this will be discussed with the investigator. If the investigator determines, in his/her clinical judgment, a treatment is appropriate the fCO₂ laser treatment will be performed. The patient will score discomfort using the VAS. The provider will score the difficulty of administering the treatment using the VAS.

Visit 9 – 30 Month Follow up (6 months +/- 2 weeks after Visit 8)

Current medications and AEs will be assessed. Urine dipstick, and urine culture will be performed, if indicated. UTI symptoms will be assessed. The patient will complete a PGI-I for symptom improvement, VSQ, I-QOL, QUID, OAB-q SF, FSFI, GAD-7 and PHQ-8. The patient will complete a three-day voiding diary within 1 week prior to Visit 10, which will be collected at Visit 10.

Visit 10 – 3 Year Follow up (6 months +/- 2 weeks after Visit 9)

Current medications and AEs will be assessed. Urine dipstick, and urine culture will be performed, if indicated. UTI symptoms will be assessed. Urine pregnancy test will be done in women of childbearing capability. The patient will complete a PGI-I for symptom improvement, VSQ, I-QOL, QUID, OAB-q SF, FSFI, GAD-7 and PHQ-8. A vaginal exam, including a cough stress test and VHIS, will be performed. A vaginal swab will be collected for wet mount and examined microscopically for presence of lactobacillus. If the patient feels her symptoms have returned and she requests a repeat treatment this will be discussed with the investigator. If the investigator determines, in his/her clinical judgment, a treatment is appropriate the fCO₂ laser treatment will be performed. The patient will score discomfort using the VAS. The provider will score the difficulty of administering the treatment using the VAS.

VAS. If a treatment is given, the participant will be instructed to follow up with the practitioner per standard of care. Visit 10 will be the final visit.

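### UTI frequency is evaluated at Visits 4 and 10, but dedicated UTI checks thin from about 6 to 2.4 per woman-year between them, and no item counts infections since the last contact

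*Combined protocol and SAP*

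**What the plan says.** The table under Objectives and Outcomes lists "Change in the frequency of UTI occurrences" as a secondary outcome and has the secondary outcomes evaluated at Visit 4 (6 months) and Visit 10 (36 months). It gives no case definition, data source or counting window.

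Section II sets the follow-up pattern: "The patient will follow up every three months for the first year, then every six months for the following two years". The treatment visits come closer together: Visit 2 is "6 weeks +/- 2 weeks after Visit 1" and Visit 3 is "6 weeks +/- 2 weeks after Visit 2". At each visit after the first the text repeats the same item: "Urine dipstick, and urine culture will be performed, if indicated. UTI symptoms will be assessed". The Visit 1 text describes the symptom assessment as presence or absence of named symptoms, with no look-back period. For the call four weeks after Visit 3, the text reads "Research staff will contact the patient by phone to assess for AEs and administer the PGI-I for overall urogenital symptoms and Perception of Monetary Value", with no UTI item.

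Other parts of the plan could also yield UTI information. Section IV has adverse events and concomitant medications queried at each visit, and names patient report and the electronic medical record among the data sources. Neither statement is linked to the UTI outcome.

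Section V promises descriptive statistics and possible paired t tests from baseline to Visit 4. It has no rate per unit of time and no allowance for how often urine was checked.

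**The concern.** An infection found only because urine was tested, or symptoms were asked about, on a visit day is found in proportion to the number of visit days. If such findings feed the UTI frequency, an unchanged infection rate will appear to decline as visits spread out. There is no comparison group followed on the same schedule to show that the decline is an artefact. The error runs towards apparent lasting benefit at 36 months, in a study that enrols some women specifically for recurrent UTI.

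The gap may also be impossible to repair at analysis. No scheduled item asks for UTIs since the last contact. The visit text for Visits 2 to 10 asks for current medications, so an antibiotic course finished months earlier need not be recorded. The protocol does not say whether a UTI in a woman enrolled for recurrent UTI counts as an adverse event. When Visits 4 to 10 are replaced by phone or mail, the items listed include neither a urine test nor the UTI symptom check, so late ascertainment can be thinner still.

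**Working it through.** The plan gives no UTI rate or ascertainment figure to reproduce. The check counts scheduled UTI checks from the visit text. In the available copy the schedule table shows a mark in nearly every cell, including urine tests at the phone call. That looks like a reading fault, so the table's cells are not used.

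**1. Check frequency.** The intervals are 6 weeks, 6 weeks, three of 3 months (Visits 3 to 6) and four of 6 months (Visits 6 to 10). With 3 months = 13.04 weeks and a year = 52.18 weeks, Visit 4 falls at week 25.0, Visit 6 at week 51.1 and Visit 10 at week 155.5. The Visit 1 check is left out because it precedes the first treatment.

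| Period | Checks | Length | Checks per woman-year |
|---|---|---|---|
| Visit 1 to 4 | 3 (Visits 2, 3, 4) | 25.0 weeks | 6.25 (6.0 on a nominal 6 months) |
| Visit 4 to 6 | 2 (Visits 5, 6) | 6 months | 4.0 |
| Visit 6 to 10 | 4 (Visits 7 to 10) | 24 months | 2.0 |
| Visit 4 to 10 | 6 (Visits 5 to 10) | 30 months | 2.4 |

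**2. Fall in visit-found infections.** Expected visit-found infections per year = checks per year × true incidence × detectable duration. With incidence and duration constant, the ratio between periods is the ratio of check frequencies:
- Against Visits 4 to 10: 6.0/2.4 = 2.5 (6.25/2.4 = 2.6).
- Against Visits 6 to 10: 6.0/2.0 = 3.0 (6.25/2.0 = 3.1). Over the allowed visit windows this runs from 2.3 to 4.4.

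**3. Effect on total UTI frequency.** Let s be the share of infections captured from history or records whatever the visit spacing, and f = checks per year × detectable days / 365.25. The share of all infections counted is s + (1 − s) × f. Neither s nor the detectable duration is in the documents, so both are assumptions. At 7 days:
- Visits 1 to 4: f = 6.25 × 7/365.25 = 0.120.
- Visits 6 to 10: f = 2.0 × 7/365.25 = 0.038.

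| s | Counted, Visits 1–4 | Counted, Visits 6–10 | Spurious fall |
|---|---|---|---|
| 0.30 | 0.30 + 0.70 × 0.120 = 0.384 | 0.30 + 0.70 × 0.038 = 0.327 | 15% |
| 0.50 | 0.50 + 0.50 × 0.120 = 0.560 | 0.50 + 0.50 × 0.038 = 0.519 | 7% |
| 1.00 | 1.000 | 1.000 | 0% |

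The same formula with 3 to 14 detectable days gives 7% to 24% at s = 0.30 and 3% to 13% at s = 0.50. Against Visits 4 to 10, where f = 2.4 × 7/365.25 = 0.046, the 7-day falls are 13% at s = 0.30 and 7% at s = 0.50.

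**4. Symptom-free positives.** At Visit 0, culture requires both symptoms and a positive dipstick. The footnote to the Schedule of Activities requires only a positive dipstick. If symptom-free positives were cultured and counted, they would add (share positive per check) × (checks per year), even with every true episode captured. Take an assumed true rate of 0.5 UTIs per year and 10% positive per check:
- Visits 1 to 4: 0.5 + 0.10 × 6.25 = 1.13 per year.
- Visits 6 to 10: 0.5 + 0.10 × 2.0 = 0.70 per year, a 38% fall.

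The fall is 26% at 5% positive and 49% at 20% positive. At 4 UTIs per year (the entry threshold for recurrent UTI) and 10% positive, the rates are 4.63 and 4.20, a 9% fall.

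**The case against.** The strongest reply is that the plan never says UTIs are counted only from visit-day tests. Adverse events and medications are asked about throughout, and the medical record is a data source. The entry threshold of 4 or more UTIs in a year can only come from history, so a change from baseline more naturally uses history at follow-up too. Counting visit-day findings alone would record about 12% of infections at 7 days' detectability even in the early period, and no one is likely to intend that. This stands, and it is why the size of the bias is a range that reaches zero. It does not close the gap, because nothing in the plan requires the history to be collected for this outcome.

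A second reply is that symptom-free positives are not UTIs, since the exclusion criterion for current UTI requires both a positive culture and reported symptoms. That is the only such description in the documents. It is written for eligibility, and the outcome does not adopt it.

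Third, Section V is descriptive, names no test of Visit 4 against Visit 10, and fixes no rate. Raw numbers of checks do not fall: 3 up to Visit 4 and 6 from Visit 4 to Visit 10. An unadjusted count over those unequal periods could therefore err upwards. This also stands, so the direction stated here applies to annualised rates.

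Finally, the Visit 10 result is hard to read as durability in any case, because repeat laser is available at 1 and 2 years and the advice against starting UTI prevention covers only the first six months. That limits what a repair can deliver. It does not excuse an avoidable further bias in the same direction.

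**Conclusion.** The point holds with a bounded size. Dedicated UTI checks fall from about 6 to 2.4 per woman-year between the two evaluation points, and to 2.0 after Visit 6. At a constant true rate, annualised infections found only by a visit-day check fall about 2.5-fold (3-fold against Visits 6 to 10). In total UTI frequency, the spurious fall against Visits 6 to 10 is about 15% at 30% between-visit capture, 7% at 50% and near 0% at full capture, assuming 7 detectable days. Counted symptom-free positives would add to it.

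Three stronger readings are tempting and not supported:
- **That reported UTI frequency must fall threefold between Visits 4 and 10.** Threefold leaves out Visits 5 and 6. It also applies only to visit-found infections, expressed per year, with nothing else captured.
- **That a 68% spurious fall is the expected size.** That is the same zero-capture extreme (1 − 2.0/6.25), and no part of the plan adopts such a count.
- **That the early rate is inflated relative to pre-treatment history.** With visit-day detection alone, 4 UTIs per year would show as 4 × 0.120 = 0.48, far below history.

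This is a change worth making to a secondary outcome. It does not affect the primary endpoint.

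**What to change.** **Data collection.** At every visit and every phone or mail contact, ask for all UTIs diagnosed since the last contact, with date and culture result, and check the medical record. Record the same history for a fixed pre-treatment period, so that baseline and follow-up are counted alike.

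**Section V.** Define the outcome as symptomatic UTI episodes per woman-year over stated fixed periods. Report infections first found by a scheduled study dipstick separately, and do not compare them between periods with different visit spacing.

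**Cost.** A short question at each contact, a record check and a few sentences in the protocol and Section V, with no new visit or test. The counted UTI rate will be somewhat lower, because dipstick-found infections are reported apart. For women already enrolled, earlier intervals would have to be rebuilt from records and recall, so the change is worth most if made early.

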 - currently implanted synthetic pelvic mesh, sling, or tape
 - current or previous genital cancers
 - radiation to the vaginal or colo-rectal tissue
 - currently pregnant or less than 3 months following pregnancy
 - undiagnosed vaginal or cervical lesions

- Patients who have received vaginal fCO₂ laser treatment within the past 12 months
- Patients treated with vaginal estrogen within the past 3 months
- Patients with undiagnosed vaginal bleeding
- Active vulvar or vaginal infection, including herpes, candidiasis, etc.
- Current UTI, confirmed by positive urine culture and patient-reported UTI symptoms
- Pelvic or vaginal surgery within the past 9 months
- Pelvic organ prolapse beyond the introitus
- Patient possesses any other characteristics that, per the investigator's judgment, deems them unsuitable (i.e. may increase patient's risk, may affect the conduct of the study, etc.) for the treatment and/or study
- Participation in an investigational trial that used a study treatment, medication and/or biologic within 6 months or less prior to the date of the screening visit

Deferral

Patients may be deferred and rescreened at a later date under the following conditions:

- Patients with active vulvar or vaginal infections may be rescreened after treatment
- Patients with an active UTI may be rescreened after treatment
- Patients with undiagnosed vaginal bleeding may be rescreened after complete work-up, treatment and resolution of vaginal bleeding
- Patients pregnant within the past 3 months
- Patients who have received vaginal fCO₂ laser treatment within the past 12 months
- Patients treated with vaginal estrogen within the past 3 months
- Patients with recent pelvic or vaginal surgery within the past 9 months

Study Visits

Visit 0 – Baseline

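### The 36-month summary pools women with three, four or five laser treatments and any new therapy, so it cannot show how long the initial course lasts

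*Combined protocol and SAP*

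**What the plan says.** - **Endpoint.** The Objectives and Outcomes table places the primary endpoint at Week 16. It lists Visit 4 and Visit 10 as secondary endpoints; for the latter: "Primary and secondary outcomes will be evaluated again at Visit 10 (36-month follow-up").
- **Repeat laser.** Section II: "The patient will be offered a repeat treatment at 1, 2 and 3 years if initial treatment efficacy has decreased". The entries for Visits 6, 8 and 10 under Study Visits make this depend on the woman feeling that symptoms are back, her request, and the investigator's judgment. At each of these visits the laser is listed after the questionnaires and examination.
- **Other therapy.** Section II advises women against "starting vaginal or systemic hormone therapy or use of new vaginal lubricants during the first six months of the study", against "starting any other preventative therapies for UTIs including antibiotic suppression, cranberry supplements, or d-mannose during the first six months of the study", and against "starting any new treatments (i.e. pharmacologic, physical therapy) for overactive bladder (OAB) or stress urinary incontinence (SUI) during the first six months of the study". No such advice is given for later months.
- **Analysis.** Section V promises descriptive statistics on everything collected. It summarises the cohort as a whole, with subgroups by presenting complaint only. Paired t tests from baseline to Visit 4 are optional. Missing values are not replaced. No summary is planned by number of laser treatments or by new therapy.

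**The concern.** Re-treatment depends on the outcome: the women whose benefit has faded are the ones who become eligible. A pooled Visit 10 figure therefore mixes benefit that has lasted since the initial course with benefit that may have been restored by another laser treatment or a new therapy. The plan separates the initial course from repeat treatment when it runs the study, but not when it analyses it.

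The background section cites calls for longer follow-up, so a reader may well take the 36-month figure as the durability of three treatments. Read that way, it would be too favourable to the extent that the added therapy still helps at Visit 10.

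**Working it through.** **Inputs.** Three initial treatments (Visits 1 to 3), repeat-laser occasions at Visits 6, 8 and 10, and the visit windows all come from Section II. Planned enrolment: "We anticipate enrolling approximately 100 women in this study". The documents give no uptake of repeat laser or new therapy, no effect of either and no dropout rate. Section V has no power calculation, so there is no planned figure to reproduce.

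**1. Treatments before the Visit 10 assessment.** Total = 3 + a + b, with a and b each 0 or 1 for Visits 6 and 8. The four possible histories give 3 (one history), 4 (two) or 5 (one). A Visit 10 laser is listed after that visit's assessments and has no later study visit, so it does not count.

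**2. Which results can be affected.** Take 3 months = 13 weeks and 6 months = 26 weeks, with visits in window, counted from Visit 1:
- Week 16 call: (6±2) + (6±2) + (4±1) = 16±5, or 11–21 weeks.
- Visit 4: (6±2) + (6±2) + (13±2) = 25±6, or 19–31 weeks.
- Visit 5: 38±8, or 30–46 weeks.
- Visit 6: 51±10, or 41–61 weeks.

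Repeat laser: the Week 16 call and Visits 4, 5 and 6 come before it. Of the seven follow-up visits (4 to 10), three are free of it and four (7 to 10) are not.

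New therapy: six months from Visit 1 ends at week 26, inside the Visit 4 window. If the six months start at Visit 0, with Visit 1 four weeks later, they end at week 26 − 4 = 22, before the nominal Visit 4 at week 25. The restriction is also only advice. New therapy can therefore affect results from Visit 4.

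**3. How mixed the group could be (illustration).** Assume each woman has probability r of repeat laser at each of Visits 6 and 8, independently. Per 100 women, the split into 3/4/5 treatments is 100(1−r)² / 200r(1−r) / 100r²:

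| Assumed r | 3 / 4 / 5 treatments | Any repeat |
|---|---|---|
| 10% | 81 / 18 / 1 | 19 |
| 30% | 49 / 42 / 9 | 51 |
| 50% | 25 / 50 / 25 | 75 |

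This shows the mix, not a bias.

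**4. Bias if the pooled mean is read as durability.** Shift = p × d, where p is the share with added therapy and d its average remaining effect at Visit 10. If d = 0, the shift is 0. A Visit 6 laser lies 4 × (26±2) = 96–112 weeks before Visit 10, and a Visit 8 laser 2 × (26±2) = 48–56 weeks before. Visits 7 and 9 fall only 24–28 weeks after a possible repeat laser. Entry excludes women with "laser treatment within the past 12 months". The plan does not call that a washout, but d may be small for Visit 6 lasers.

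**5. Why the fix needs one denominator (illustration, all counts assumed).** Take 100 women given Treatment 1. Of these, 25 have added therapy, all are seen at Visit 10, and 15 are improved. Of the other 75, 15 are missing and 45 of the 60 seen are improved.
- Persistence (improved and no added therapy): 45/100 = 45% (Wilson 95% CI 35.6–54.8) with the missing counted as not persisting; 60/100 = 60% (50.2–69.1) with them counted as persisting.
- Pooled, observed women only: (45 + 15)/85 = 70.6%. Set beside the bounds, the gap is 25.6 or 10.6 points, which mixes dropout with re-treatment.
- Pooled, same denominator and bounds: 60/100 = 60% and 75/100 = 75%. The gap is now 15 points at both bounds.
- A bare count of women without added therapy would read 75%, because it includes women who never improved or were not seen.

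**The case against.** The strongest defence is that nothing is mislabelled. This is an uncontrolled descriptive study, and no stated objective is the duration of the initial course. The pooled Visit 10 result is a legitimate description of care as delivered. The primary endpoint and the only named test precede any repeat laser. The promise to describe all data can cover counts of repeat lasers and medications. A composite persistence measure also depends on what is counted: a new lubricant or a cranberry supplement could make a failure of a woman who is still improved.

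Most of this stands and limits the point. There is no contradiction in the plan, and the pooled summary should stay. But a general promise to describe the data does not commit to showing outcomes by re-treatment or new therapy, and neither does the planned exploration of complications. The dependence on definitions is a reason to fix the list of counted therapies beforehand.

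Stronger readings that a reader might infer, and that the documents do not support:
- *The 36-month result is biased upward.* Neither uptake nor remaining effect is given, and the plan does not present the figure as durability.
- *The gap between pooled and persistence proportions measures that bias.* It is a difference between two definitions. In the illustration it would be 15 points even if the added therapy did nothing, and it takes that simple form only with complete data or matched denominators.
- *The primary endpoint or the 12-month results are compromised by repeat laser.* By the listed order of procedures, they are not.
- *Women without added therapy show the true durability.* They are selected for lasting response.

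**Conclusion.** The point holds as an inexpensive improvement to Section V. As planned, the Visit 10 summary cannot distinguish lasting benefit of the initial course from benefit after repeat laser or new therapy. Repeat laser is confined to Visits 7 to 10, of which only Visit 10 is a named endpoint. New therapy can enter from Visit 4.

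The size of any bias in a durability reading is unknown and may be zero. The uptake rates and counts used above are assumptions, not predictions.

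The conclusion rests on three conditions: visits are in window; *three, four or five* refers to women who completed the initial course; and assessments at Visits 6, 8 and 10 are made before any laser that day. The listed order supports the last condition, but the protocol says so expressly only for the Visit 1 questionnaires.

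**What to change.** In Section V:

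1. Keep the pooled Visit 10 summary and label it *initial three-treatment course with on-demand repeat laser and other therapy as used*.
2. Tabulate the number and timing of repeat lasers and new therapies. Show outcomes by repeat-laser status from Visit 7 and by new-therapy status from Visit 4, and state that women without added therapy are a selected group.
3. Add a supplementary persistence proportion at Visits 6, 8 and 10 among all women given Treatment 1. It requires a PGI-I improvement category fixed in advance AND no earlier repeat laser or new therapy from a list fixed in advance.
   - A woman with an earlier event counts as not persisting even if she is later missing.
   - Give a 95% CI, the number otherwise missing, and bounds with all of them counted each way. Show the pooled proportion with the same denominator and the same bounds. The rule against replacing missing values stays in force for the main summaries.
   - State that the figure is conservative, because repeat laser may follow only a partial loss of benefit and a woman who is still improved may start a listed therapy.
4. Define when the six-month advice period starts, and reconcile that passage with the Visit 4 window.

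**Cost.** Some wording and a few extra tables, with no extra visits and no change to who is re-treated. Item 2 needs start dates for new therapies, including physical therapy and supplements. The CRF is not among the documents, so a short added item may be needed. The persistence figure may be less favourable than the pooled one.
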